**12.7.2.1. Handling of Missing and Partial Dates**

Element	Reporting Detail
General	
 
● Partial dates will be displayed as captured in subject listing displays.
 

Adverse Events	
 
● The eCRF allows for the possibility of partial dates (i.e., only month and year) to be recorded for AE start and end dates; that is, the day of the month may be missing. In such a case, the following conventions will be applied for calculating the time to onset and the duration of the event:                             
 
○ Missing Start Day: First of the month will be used unless this is before the start date of study treatment; in this case the study treatment start date will be used and hence the event is considered On-treatment as per Appendix 4: Study Phases and Treatment Emergent Adverse Events.
 
○ Missing Stop Day: Last day of the month will be used, unless this is after the stop date of study treatment; in this case the study treatment stop date will be used.
 
 
 
● Completely missing start or end dates will remain missing, with no imputation applied. Consequently, time to onset and duration of such events will be missing.
 

Concomitant Medications/ Medical History	
 
● Partial dates for any concomitant medications recorded in the CRF will be imputed using the following convention:                             
 
○ If the partial date is a start date, a '01' will be used for the day and 'Jan' will be used for the month
 
○ If the partial date is a stop date, a '28/29/30/31' will be used for the day (dependent on the month and year) and 'Dec' will be used for the month.
 
 
 
● The recorded partial date will be displayed in listings.
 

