Vital signs		X	X 	X	X	X 	X	X 	X	X 	X	X	X	X	X	1. Test to be performed pre-dose prior to spirometry and post-dose prior the 12-lead ECG.
Dispense paper Medical Problems/Medications Taken worksheet		X	X	X	X	X	X	X	X	X	X	X	X	X		
Review paper Medical Problems/Medications Taken worksheet			X	X	X	X	X	X	X	X	X	X	X	X	X	

Procedure	Pre-Screening 	Screen Run-in	Treatment Period										Follow-up Period  (± 3 days)			Notes
			± 2 days			± 3 days							12	13	14	
Visit	0	1	2 	3	4	5	6	7	8	9	10	11 (ETP or EW)	12	13	14	1. Pre-screening and screening can occur on the same day 2. FU period to start 4 weeks after ETP or EW visit. 3. Visit 2 = Day 1 (first dose of IP).
Week	-4~-2	-2	0	1	2	4	6	8	10	12	14	16	20	24	28	
Study Day	-28~-14	-14	1	8	15	29	43	57	71	85	99	113				
AE/SAE review	X 	X 	←-----→										X	X	X	1. At V0 and V1 collect only SAEs considered as related to study participation.
Concomitant medication review	X	X	←-----→										X	X	X	
Questionnaires																
ACQ-5		X	X													After randomization, ACQ5 will be completed by the participants every 7 days.
SGRQ			X			X		X		X		X				
Study Treatment																
Double blind Study Treatment (IP)			X			X		X		X						Patients will remain in the clinic for monitoring for at least 2 hours after the end of infusion.
FP/Sal (500/50) dispensing		X	X													
FP (mcg) dispensing					500	250	100	50								
Dispense albuterol (as needed)		X	X	X	X	X	X	X	X	X	X	X				

Procedure	Treatment Period										Follow-up  (± 3 days)			Notes
	± 2 days			± 3 days										
Visit	2 	3	4	5	6	7	8	9	10	11 (ETP or EW)	12	13	14	1. Visit 2 = Day 1 (first dose of IP). 2. FU period to start 4 weeks after ETP or EW visit.
Week	0	1	2	4	6	8	10	12	14	16	20	24	28	
Study Day	1	8	15	29	43	49	71	85	99	113				
Double blind Study Treatment (IP)	X			X		X		X						
PK sample	X 	X	X	X 		X 		X 		X	X	X	X	1. Pre dose and post dose. 2. Post dose only. 3. Pre dose only. Pre-dose samples within 2 hours from the planned dosing time. Post-dose samples as soon as possible after end of infusion but must be taken within 4 hours.
Free and total sST2	X 	X	X	X 		X 		X 		X	X	X	X	
Immunogenicity sample	X 		X	X 		X 		X 		X	X	X	X	

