### 12.6.2. Study Population

Age
Date of birth will be set as PPD YYYYY where YYYYY is the year of birth taken from the CRF. For participants who attended a screening visit, age will be calculated at the screening visit date. For pre-screen failures, age will be calculated at the pre-screening visit date.
Body Mass Index (BMI)
BMI = Weight (kg) / Height(m) 
Treatment Misallocations
To allocate treatment, the number of doses of GSK3772847 and Placebo that were given will be calculated, and the subject will be assigned to whichever treatment has the higher number. The only exception will be when both treatments were given equally, in which case the subject will be assigned their randomised treatment.
Early Withdrawal from Study Treatment Date

The eCRF captures the study treatment start and end, however this is the physical time and date of the infusion. The date of early withdrawal from study treatment is not captured and should therefore be calculated as follows:
 
 
• If the participant withdrew from treatment due to loss of asthma control then the date of early withdrawal from study treatment is set to the date of loss of asthma control.
 
• If the participant withdrew due to an AE/SAE/Death then withdrawal date is set to the AE/SAE onset date (all deaths should be reported as serious adverse events)
 
• If the participant withdrew from study treatment (for a reason other than those above) during the first 10 weeks of the study i.e. during the down titration of the background medications, then the FP/SAL or FP discontinuation date should be used as the date of withdrawal from study treatment.
 
• For participants who withdraw from study treatment (for a reason other than those above) between Week 10 and Week 16, there is no information on when they withdrew as they are no longer taking background medications. The date of early withdrawal from study treatment should therefore be set to the maximum of date of last dose of FP and date of last dose +1. This is because no more information is available other than the fact that they had not lost control prior to completing the down titration or prior to receiving their final dose of IP.
 

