## 12.10.7. Safety Tables

Safety: Tables					
No.	Population	IDSL / Example Shell	Title	Programming Notes	Deliverable [Priority]
Adverse Events (AEs)					
3.1.	SAFF_ALL	SAFE_T01	Overview of On-treatment Adverse Events During the Study		ETP, SAC
3.2.	SAFF_ALL	AE1	Summary of All On-treatment Adverse Events by System Organ Class and Preferred Term	ICH E3	ETP, SAC
3.3.	SAFF_ALL	AE1	Summary of All Post-treatment Adverse Events by System Organ Class and Preferred Term	ICH E3	ETP, SAC
3.4.	SAFF_ALL	AE1	Summary of All On-treatment Adverse Events Leading to Permanent Discontinuation of Study Treatment by System Organ Class and Preferred Term	ICH E3	ETP, SAC
3.5.	SAFF_ALL	AE1	Summary of All On-treatment Adverse Events Leading to Withdrawal from Study by System Organ Class and Preferred Term	ICH E3	ETP, SAC
3.6.	SAFF_ALL	AE1	Summary of All On-treatment Fatal Adverse Events by System Organ Class and Preferred Term	ICH E3	ETP, SAC
3.7.	SAFF_ALL	AE3	Summary of All On-treatment Common ( $\geq 3\%$ ) Adverse Events by Overall Frequency	ICH E3	ETP, SAC
3.8.	SAFF_ALL	AE1	Summary of All On-treatment Drug-Related Adverse Events by System Organ Class and Preferred Term	ICH E3	ETP, SAC
3.9.	SAFF_ALL	AE15	Summary of All On-treatment Common ( $\geq 3\%$ ) Non-serious Adverse Events by System Organ Class and Preferred Term (Number of Participant and Occurrences)	FDAAA, EudraCT	ETP, SAC
3.10.	SAFF_ALL	AE1	Summary of All Pre-treatment Serious Adverse Events by System Organ Class and Preferred Term		ETP, SAC

Safety: Tables					
No.	Population	IDSL / Example Shell	Title	Programming Notes	Deliverable [Priority]
3.11.	SAFF_ALL	AE1	Summary of All On-treatment Serious Adverse Events by System Organ Class and Preferred Term	ICH E3	ETP, SAC
3.12.	SAFF_ALL	AE1	Summary of All Post-treatment Serious Adverse Events by System Organ Class and Preferred Term	ICH E3	ETP, SAC
3.13.	SAFF_ALL	AE16	Summary of All On-treatment Serious Adverse Events by System Organ Class and Preferred Term (Number of Participants and Occurrences)	FDAAA, EudraCT	ETP, SAC
3.14.	SAFF_ALL	AE1	Summary of All On-treatment Serious Adverse Events Leading to Permanent Discontinuation of Study Treatment by System Organ Class and Preferred Term	IDSL	ETP, SAC
3.15.	SAFF_ALL	AE1	Summary of All On-treatment Serious Adverse Events Leading to Withdrawal from Study by System Organ Class and Preferred Term	IDSL	ETP, SAC
Adverse Events of Special Interest (AESIs)					

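### The rules for AE dates with a missing day can put the stop before the onset and can declare an SAE from a month wholly before dosing On-treatment

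*SAP*

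**What the plan says.** SAP 12.7.2.1 covers AE dates recorded as month and year only. Its stated purpose is to derive how long after treatment start an AE began and how long it lasted.

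- If the start lacks its day: "First of the month will be used unless this is before the start date of study treatment". Where the first of the month is the earlier of the two, the rule goes on: "in this case the study treatment start date will be used and hence the event is considered On-treatment", with a reference to Appendix 4.
- If the stop lacks its day: "Last day of the month will be used, unless this is after the stop date of study treatment". Where month-end is the later of the two, the treatment stop date replaces it.

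SAP 12.6.2 explains what the treatment dates are: "The eCRF captures the study treatment start and end, however this is the physical time and date of the infusion". SAP 12.4.2 counts an AE as treatment-emergent if its onset lies between treatment start (inclusive) and 28 days after treatment stop. SAP 12.4.1, for all non-efficacy data, classes a date on or before treatment start as Pre-treatment.

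The schedule in SAP 12.2.1 continues AE review through the follow-up visits to Week 28. For the period before dosing it says: "At V0 and V1 collect only SAEs considered as related to study participation". Those events have their own display, Table 3.10 in SAP 12.10.7: "Summary of All Pre-treatment Serious Adverse Events by System Organ Class and Preferred Term".

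**The concern.** The stop rule treats the last infusion as if nothing could end after it. The SAP's own framework says otherwise: the treatment-emergent window runs 28 days past that infusion, and Tables 3.3, 3.12, 3.18 and 3.19 report post-treatment events. The rule has no floor at the AE onset, so it can return a stop date earlier than the start. The concomitant-medication rule in the same table imputes stop dates without any such cap.

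The start rule is an ordinary conservative convention when the recorded month is the month of first dosing, because the true day might fall on either side of the infusion. As written it also applies to any earlier month, where every possible day precedes dosing. At stake are the derived durations of AEs with a missing stop day, and the treatment attribution of a pre-dose SAE with a missing start day.

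**Working it through.** The SAP gives no figure to reproduce; the check applies its date rules literally.

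**Inputs.** Infusions at Weeks 0, 4, 8 and 12, the last on Day 85 (SAP 2.4 and 12.2.1). Week 16 is Day 113, so Week 28 is Day 113 + 84 = 197. For illustration I assume a first infusion on 5 March 2018, which puts the last on 28 May 2018 and Week 28 on 17 September 2018. I take duration as stop − start + 1; the SAP gives no formula for AE duration.

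**Stop rule, general argument.** If onset is after the last infusion, the end of the stop month cannot be earlier than onset, so it too is after the last infusion. The rule then always fires and sets the stop to the last infusion, before onset. Onset days exposed: 197 − 85 = 112, and all 112 are reversed.

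**Stop rule, examples.**

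| AE start | Recorded stop | Imputed stop | Duration as written | Duration with uncapped month-end |
|---|---|---|---|---|
| 10 July | July | 28 May | −42 | 22 |
| 11 June (Week 14, treatment-emergent) | June | 28 May | −13 | 20 |
| 20 May (before last infusion) | June | 28 May | 9 | 42 |

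The third row is shortened, not reversed.

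**Alternative reading.** If treatment stop meant last infusion + 28 days (Day 113), onsets from Day 114 to Day 197 would still be reversed: 197 − 113 = 84 of 112. That reading does not rescue the rule.

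**Start rule.** Take a pre-dose SAE dated February 2018, with first dose on 5 March. The first of February precedes treatment start, so the onset becomes 5 March, study Day 1. Its status then depends on the section read:

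- 12.7.2.1: On-treatment.
- 12.4.2: treatment-emergent, since onset on the start date counts.
- 12.4.1: Pre-treatment, since a date equal to treatment start still falls in that phase.

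If the stop is also recorded as February, it is imputed as 28 February and the duration is −4 days.

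**How much of the pre-dose period lies in an earlier month.** Assume first-dose dates spread evenly over the 365 days of 2018. With a 14-day pre-dose period the share is 12 × (14 + 13 + … + 1) / (365 × 14) = 1,260 / 5,110 = 25%. With 28 days it is 12 × (28 + 27 + … + 1) / (365 × 28) = 4,872 / 10,220 = 48%. These are shares of days, not of events.

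**The case against.** The strongest reply is that little reported output depends on these rules, and most of that stands.

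- **Stop rule.** A reader might infer that it undermines the follow-up safety analysis, which SAP 3.1 describes as the aim of the final analysis. The document does not support that. Treatment-emergence depends on onset, no phase definition uses the AE stop date, the event-rate formula in SAP 12.6.4 uses event counts and exposure, and no title among Tables 3.1 to 3.19 names duration or time to onset. The mock shells are not included, so a duration column somewhere cannot be excluded, but none is shown. Listings display partial dates as captured.
- **Size.** The 112 days are 57% of a 197-day participation (112/197). A reader might take this as the share of AEs affected. It is a share of calendar days for one dosing pattern; only AEs lacking the day are affected.
- **Start rule.** Only study-related SAEs are collected before dosing, and to be misplaced one must also lack its start day and fall in an earlier month. The error goes towards On-treatment, so it does not hide an on-treatment event. Entry to the AESI tables would also need a qualifying term.
- **Table 3.10.** A reader might infer that such an SAE necessarily leaves this table. That depends on whether 12.4.1 or 12.4.2 is programmed, and the SAP does not settle it.

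None of this makes either rule correct. No other section adds a floor at onset or a same-month condition.

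**Conclusion.** Both rules are wrong as written, and the consequences are limited. For an AE starting after the last infusion with a missing stop day, the imputed stop always precedes onset; for one straddling that infusion, duration is truncated. The damage is confined to derived AE duration. Separately, a study-related pre-dose SAE dated only to an earlier calendar month is declared On-treatment and is treatment-emergent under 12.4.2, while 12.4.1 would still class the imputed date as Pre-treatment.

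This rests on reading treatment start and stop as infusion dates, as 12.6.2 states; adding 28 days to the stop reduces the stop-date fault but does not remove it. The number of AEs with partial dates is not stated. I expect it to be small, particularly before dosing, so this is a correction of date logic and not a threat to the trial's safety conclusions.

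**What to change.** In SAP 12.7.2.1:

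- **Missing stop day:** use the last day of the recorded month, without a cap at the last infusion, and never earlier than the AE start date. A cap at death or last study contact is optional.
- **Missing start day:** use the treatment start date only when the recorded month and year are those of the first infusion. For an earlier month, use the first of that month and keep the event Pre-treatment.

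In SAP 12.4.1 and 12.4.2, reconcile how an AE dated on the treatment start date is classified, so that Table 3.10 and the on-treatment tables follow one definition.

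With these rules the February SAE in the example starts on 1 February 2018 and is Pre-treatment and not treatment-emergent. The cost is a few lines of SAP wording and an edit to the AE date and phase derivations; no additional data are needed.

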**12.8. Appendix 8: Values of Potential Clinical Importance**

Values of potential clinical importance will not be used in this study, instead normal reference ranges of “Low”, “Normal” and “High” will be used.

## 12.9. Appendix 9: Abbreviations & Trade Marks

### 12.9.1. Abbreviations

Abbreviation	Description
ADaM	Analysis Data Model
AE	Adverse Event
A&R	Analysis and Reporting
CDISC	Clinical Data Interchange Standards Consortium
CI	Confidence Interval
CS	Clinical Statistics
CSR	Clinical Study Report
CV b / CV w	Coefficient of Variation (Between) / Coefficient of Variation (Within)
DBF	Database Freeze
DBR	Database Release
DOB	Date of Birth
DP	Decimal Places
eCRF	Electronic Case Record Form
EMA	European Medicines Agency
FDA	Food and Drug Administration
FDAAA	Food and Drug Administration Clinical Results Disclosure Requirements
GSK	GlaxoSmithKline
IA	Interim Analysis
ICH	International Conference on Harmonization
IDSL	Integrated Data Standards Library
IgE	Immunoglobulin E
IMMS	International Modules Management System
IP	Investigational Product
mIT	Modified Intent-to-Treat excluding GCP non-compliant subjects
mITT_LoC	Modified Intent-to-Treat excluding GCP non-compliant subjects (Loss of Control)
MMRM	Mixed Model Repeated Measures
PCI	Potential Clinical Importance
PD	Pharmacodynamic
PDMP	Protocol Deviation Management Plan
PK	Pharmacokinetic
QC	Quality Control
QTcF	Frederica's QT Interval Corrected for Heart Rate
RAP	Reporting & Analysis Plan
RAMOS	Randomisation & Medication Ordering System
SAC	Statistical Analysis Complete
SAFF_ALL	Safety including site including GCP non-compliant subjects
SDTM	Study Data Tabulation Model
SOP	Standard Operation Procedure
TA	Therapeutic Area
TFL	Tables, Figures & Listings

**12.9.2. Trademarks**

Trademarks of the GlaxoSmithKline Group of Companies
None

Trademarks not owned by the GlaxoSmithKline Group of Companies
NONMEM
SAS

## 12.10. Appendix 10: List of Data Displays

All displays (Tables, Figures & Listings) will use the term 'Subjects' instead of "Participants".

### 12.10.1. Data Display Numbering

The following numbering will be applied for RAP generated displays:

Section	Tables	Figures
Study Population	1.1 to 1.n	1.1 to 1.n
Efficacy	2.1 to 2.n	2.1 to 2.n
Safety	3.1 to 3.n	3.1 to 3.n
Pharmacokinetic	4.1 to 4.n	4.1 to 4.n
Pharmacodynamic or Biomarker	6.1 to 6.n	6.1 to 6.n
Section	Listings	
ICH Listings	1 to x	
Other Listings	y to z	

### 12.10.2. Mock Example Shell Referencing

Non IDSL specifications will be referenced as indicated and if required example mock-up displays provided in [Appendix 11](#): Example Mock Shells for Data Displays.

Section	Figure	Table	Listing
Study Population	POP_Fn	POP_Tn	POP_Ln
Efficacy	EFF_Fn	EFF_Tn	EFF_Ln
Safety	SAFE_Fn	SAFE_Tn	SAFE_Ln
Pharmacokinetic	PK_Fn	PK_Tn	PK_Ln
Pharmacodynamic or Biomarker	PD_Fn	PD_Tn	PD_Ln

**NOTES:**

- Non-Standard displays are indicated in the 'IDSL / Example Shell' or 'Programming Notes' column as '[Non-Standard] + Reference.'

### 12.10.3. Deliverables

Delivery [Priority] 	Description
ETP [1]	End of Treatment Phase Statistical Analysis Complete
SAC [1]	Final Statistical Analysis Complete

**NOTES:**

- Indicates priority (i.e. order) in which displays will be generated for the reporting effort

## 12.10.4. Study Population Tables

Study Population Tables					
No.	Population	IDSL / Example Shell	Title	Programming Notes	Deliverable [Priority]
Subject Disposition					
1.1.	SAFF_ALL	ES8	Summary of Subject Status and Reason for Study Withdrawal	ICH E3, FDAAA, EudraCT	ETP, SAC
1.2.	SAFF_ALL	SD4	Summary of Treatment Status and Reasons for Discontinuation of Study Treatment	ICH E3	ETP, SAC
1.3.	SAFF_ALL	ES4	Summary of Subject Disposition at Each Study Epoch	ICH E3	ETP, SAC
1.4.	ASE	ES6	Summary of Screening/Run-in Status and Reasons for Screen/Run-in Failure	Journal Requirements	ETP, SAC
1.5.	Enrolled	NS1	Summary of Number of Subjects by Country and Site ID	EudraCT/Clinical Operations	ETP, SAC
1.6.	SAFF_ALL	NS1	Summary of Number of Subjects by Country and Site ID	EudraCT/Clinical Operations	ETP, SAC
Protocol Deviation					
1.7.	SAFF_ALL	DV1	Summary of Important Protocol Deviations	ICH E3	ETP, SAC
1.8.	SAFF_ALL	IE1	Summary of Inclusion/ Exclusion Deviations	ICH E3	ETP, SAC
Population Analysed					
1.9.	Enrolled	SP1	Summary of Study Populations	IDSL	ETP, SAC
Demographic and Baseline Characteristics					
1.10.	SAFF_ALL	DM1	Summary of Demographic Characteristics	ICH E3, FDAAA, EudraCT	ETP, SAC
1.11.	Enrolled	DM11	Summary of Age Ranges	EudraCT	ETP, SAC
1.12.	SAFF_ALL	DM5	Summary of Race and Racial Combinations	ICH E3, FDA, FDAAA, EudraCT	ETP, SAC
Prior and Concomitant Medications					
1.13.	SAFF_ALL	MH4	Summary of Current Medical Conditions	ICH E3	ETP, SAC

Study Population Tables					
No.	Population	IDSL / Example Shell	Title	Programming Notes	Deliverable [Priority]
1.14.	SAFF_ALL	MH4	Summary of Past Medical Conditions	ICH E3	ETP, SAC
1.15.	SAFF_ALL	SP07	Summary of Family History of Cardiovascular Disorders at Screening		ETP, SAC
1.16.	SAFF_ALL	POP_T01	Summary of Disease Duration and Exacerbation History		ETP, SAC
1.17.	SAFF_ALL	SU1	Summary of Smoking History at Screening		ETP, SAC
1.18.	SAFF_ALL	CM1	Summary of Pre-treatment Non-Asthma Concomitant Medications	ICH E3	ETP, SAC
1.19.	SAFF_ALL	CM1	Summary of On-treatment Non-Asthma Concomitant Medications	ICH E3	ETP, SAC
1.20.	SAFF_ALL	CM1	Summary of Post-treatment Non-Asthma Concomitant Medications	ICH E3	ETP, SAC
1.21.	SAFF_ALL	CM1	Summary of On-treatment Asthma Concomitant Medications	ICH E3	ETP, SAC
1.22.	SAFF_ALL	CM1	Summary of Post-treatment Asthma Concomitant Medications	ICH E3	ETP, SAC
Pre-treatment Lung Function					
1.23.	SAFF_ALL	POP_T02	Summary of Screening Lung Function	Include Pre- and Post- albuterol (salbutamol) FEV 1 , FVC, FEV 1 /FVC and % Predicted Normal and post-BD at screening %predicted. Include overall and by treatment group.	ETP, SAC
1.24.	SAFF_ALL	POP_T03	Summary of Baseline Lung Function	FEV 1 , FVC, FEV 1 /FVC and % Predicted Normal. Include overall and by treatment group.	ETP, SAC
Exposure and Treatment Compliance					
1.25.	SAFF_ALL	EX1	Summary of Exposure and Compliance to Background Therapy (FP and SAL)	ICH E3	ETP, SAC

## 12.10.5. Efficacy Tables

Efficacy: Tables					
No.	Population	IDSL / Example Shell	Title	Programming Notes	Deliverable [Priority]
Exposure					
2.1.	SAFF_ALL	EX1	Summary of Exposure to Study Treatment	ICH E3	ETP, SAC
Primary Endpoint: Loss of Asthma Control Weeks 0-16					
2.2.	mITT_LoC	EFF_T01	Summary of Loss of Asthma Control	Include overall loss of control, each component and the combination of exacerbation or inability to titrate.	ETP, SAC
2.3.	mITT_LoC	EFF_T02	Summary of On-treatment Intercurrent Events		ETP, SAC
2.4.	mITT_LoC	EFF_T03	Bayesian Analysis of Loss of Asthma Control Over Weeks 0-16 (Primary Estimand)		ETP, SAC
2.5.	mITT_LoC	EFF_T04	Frequentist Analysis of Loss of Asthma Control Over Weeks 0-16 (Primary Estimand)		ETP, SAC
2.6.	mITT_LoC	EFF_T03	Bayesian Analysis of Loss of Asthma Control Over Weeks 0-16 (Secondary Estimand)		ETP, SAC
2.7.	mITT_LoC	EFF_T04	Frequentist Analysis of Loss of Asthma Control Over Weeks 0-16 (Secondary Estimand)		ETP, SAC
Secondary Endpoint: Loss of Asthma Control Weeks 0-6					
2.8.	mITT_LoC	EFF_T03	Bayesian Analysis of Loss of Asthma Control Over Weeks 0-6 (Primary Estimand)		ETP, SAC
2.9.	mITT_LoC	EFF_T04	Frequentist Analysis of Loss of Asthma Control Over Weeks 0-6 (Primary Estimand)		ETP, SAC
2.10.	mITT_LoC	EFF_T03	Bayesian Analysis of Loss of Asthma Control Over Weeks 0-6 (Secondary Estimand)		ETP, SAC

Efficacy: Tables					
No.	Population	IDSL / Example Shell	Title	Programming Notes	Deliverable [Priority]
2.11.	mITT_LoC	EFF_T04	Frequentist Analysis of Loss of Asthma Control Over Weeks 0-6 (Secondary Estimand)		ETP, SAC
Secondary Endpoints: Time to Loss of Asthma Control					
2.12.	mITT_LoC	EFF_T05	Summary and Analysis of Time to Loss of Asthma Control (Primary Estimand)		ETP, SAC
2.13.	mITT_LoC	EFF_T05	Summary and Analysis of Time to Loss of Asthma Control (Secondary Estimand)		ETP, SAC
Secondary Endpoints: Hospitalisation and Emergency Room Visits					
2.14.	mITT	EFF_T06	Summary and Rate of Asthma-Related On-treatment Hospitalisations and Emergency Room Visits (Primary Estimand)		ETP, SAC
Secondary Endpoint: ACQ-5 and SGRQ					
2.15.	mITT	EFF_T07	Summary of Raw and Change from Baseline in ACQ-5 Total Score (Primary Estimand)		ETP, SAC
2.16.	mITT	EFF_T07	Summary of ACQ-5 Responders (Primary Estimand)		ETP, SAC
2.17.	mITT	EFF_T07	Summary of Raw and Change from Baseline in SGRQ Total Score (Primary Estimand)		ETP, SAC
2.18.	mITT	EFF_T07	Summary of SGRQ-Responders (Primary Estimand)		ETP, SAC
Secondary Endpoint: FEV1 and PEF					
2.19.	mITT	EFF_T07	Summary of Raw and Change from Baseline FEV 1 (Primary Estimand)		ETP, SAC
2.20.	mITT	EFF_T08	Analysis of Change from Baseline in FEV 1 up to Week 4 (Primary Estimand)		ETP, SAC

Efficacy: Tables					
No.	Population	IDSL / Example Shell	Title	Programming Notes	Deliverable [Priority]
2.21.	mITT	EFF_T07	Summary of Raw and Change from Baseline Fractional Exhaled Nitric Oxide (FeNO) (Primary Estimand)		ETP, SAC
2.22.	mITT	EFF_T08	Analysis of Change from Baseline in Fractional Exhaled Nitric Oxide (FeNO) up to Week 4 (Primary Estimand)		ETP, SAC
Secondary Endpoint: Exacerbations					
2.23.	mITT	EFF_T09	Summary of On-treatment Asthma Exacerbations		ETP, SAC
Secondary Endpoint: Eosinophils					
2.24.	mITT	EFF_T07	Summary of Raw and Change from Baseline in Eosinophils (Primary Estimand)		ETP, SAC
2.25.	mITT	EFF_T08	Analysis of Eosinophils up to Week 4 (Primary Estimand)		ETP, SAC
Secondary Endpoint: PEF, Daytime Symptom Score, Night-time Symptom Score and Rescue Medication					
2.26.	mITT	EFF_T010	Summary of Raw and Change from Baseline in Mean Morning Peak Expiratory Flow (PEF)		ETP, SAC
2.27.	mITT	EFF_T010	Summary of Raw and Change from Baseline in Mean Evening Peak Expiratory Flow (PEF)		ETP, SAC
2.28.	mITT	EFF_T010	Summary of Raw and Change from Baseline in Mean Daytime Asthma Symptom Score		ETP, SAC
2.29.	mITT	EFF_T010	Summary of Raw and Change from Baseline in Night-Time Awakenings Due to Asthma Symptoms		ETP, SAC
2.30.	mITT	EFF_T010	Summary of Raw and Change from Baseline in Mean Rescue Medication use (Albuterol/Salbutamol)		ETP, SAC

